### **Dose Response Modeling**

Data permitting a 4-Parameter  $E_{max}$  model will be used to characterize the %change from baseline dose-response relationship of whole liver fat in Part 2. The model structure will take the form:

$$CFB = E_0 + \frac{E_{max} \times dose^{Hill}}{ED_{50}^{Hill} + dose^{Hill}}$$

$E_0$  is the placebo effect,  $dose$  is the target randomized dose,  $E_{max}$  is the maximum effect,  $ED_{50}$  is the dose producing 50% of the maximum effect and  $Hill$  is the slope parameter.

The natural log transformed relative ratio from baseline response at the end of treatment period will be modeled with dose as a continuous variable and natural log transformed baseline whole liver fat as a covariate. The model will be applied to the LSMean results from the primary ANCOVA model utilizing a Bayesian methodology with weakly informative priors as described in Appendix 3. The posterior means and 80% credible intervals of the placebo-adjusted effect estimates at each dose will be exponentiated to obtain the predicted values of %change from baseline. Estimates of the model parameters of  $E_0$ ,  $E_{max}$ ,  $ED_{50}$  and slope and their 80% credible intervals will also be produced. In addition, the doses that result in 25% and 30% liver fat lowering will be identified along with their 80% credible intervals.

If convergence cannot be obtained or visual inspection of the data does not support a dose-response  $E_{max}$  relationship the following options will be considered in order: (1) assume the hill parameter is 1 and remove from the model (giving a 3-parameter dose-response  $E_{max}$  model) or (2) utilize alternative priors to those provided in the appendix.

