4.3.1. Projected Human PK Parameters and Effective Human Dose

In humans, PF-07202954 is predicted to have a CL_{plasma} of 3.34 mL/min/kg (hepatic clearance of 1.34 mL/min/kg; renal clearance of 2.0 mL/min/kg), F of 32% (oral absorption of 35%), V_{ss} of 2.30 L/kg, and an effective $t_{1/2}$ of approximately 8 hours.

The average total C_{eff} for PF-07202954 over the once daily dosing interval of 76.6 ng/mL (66.8 nM unbound), is equivalent to approximately IC_{85} of the in vitro human biochemical and human hepatocyte potencies. This exposure is projected with a clinical dose of 80 mg administered once daily of PF-07202954 and predicted to lower hepatic steatosis by $\geq 35\%$ following 14 days of dosing (ie, similar magnitude as observed following 14 days of

dosing of 2 other oral DGAT2i).^{11,12} At the PF-07202954 dose of 80 mg administered once daily, projected exposures are total C_{max} of 106 ng/mL and total AUC_{24} of 1840 ng•h/mL.

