## Appendix 2. List of Abbreviations

Abbreviation	Term
Abs	absolute
AE	adverse event
$Ae_{\text{tau}}$	Amount of unchanged drug recovered in urine during dosing interval
$Ae_{\text{tau}}\%$	Percent of dose recovered in urine as unchanged drug over dosing interval
ANCOVA	analysis of covariance
ANOVA	Analysis of variance
AUC	area under the curve
$AUC_{\text{inf}}$	area under the concentration-time curve from time 0 to infinity
CCI	
$AUC_{\text{last}}$	area under the concentration-time curve from time 0 to the time of the last quantifiable concentration
CCI	
$AUC_{\text{tau}}$	area under the concentration-time curve from time 0 to time $\tau$ (tau)
$AUEC_{24}$	area under the effect curve over the time of 0-24 hours post dose
BLQ	below the limit of quantitation
BP	blood pressure
CAP TM	Controlled attenuation parameter (trademarked by EchoSens ® )
$C_{\text{av}}$	average concentrations
CDISC	Clinical Data Interchange Standards Consortium
CFB	Change from baseline
CI	confidence interval
$C_{\text{last}}$	Last quantifiable plasma concentration
CL/F	apparent clearance following oral administration
$CL_r$	renal clearance
CL	Systemic clearance
CM	Composite measure
$C_{\text{max}}$	maximum observed concentration
CCI	
$C_{\text{min}}$	minimum observed concentration
CRF	case report form
CRU	clinical research unit
CSR	clinical study report
%CV	percent coefficient of variation
CYP	cytochrome P450
CCI	
$E_0$	Efficacy at 0 dose level; also treated as placebo effect
EC	ethics committee
ECG	electrocardiogram
$ED_{50}$	effective dose for 50% of the maximal efficacy
$E_{\text{max}}$	maximum response achievable

Abbreviation	Term
FDA	Food and Drug Administration (United States)
FPG	Fasting plasma glucose
FPI	Fasting plasma insulin
GCP	Good Clinical Practice
GM	Geometric mean
GMC	geometric mean concentration
GMR	Geometric mean ratio
HDL-C	high-density lipoprotein cholesterol
CCI	[REDACTED]
HR	Heart Rate
IA	Interim Analysis
ICH	International Council for Harmonisation
K el	terminal phase rate constant calculated by a linear regression of the log-linear concentration-time curve
CCI	[REDACTED]
LDL-C	low-density lipoprotein cholesterol
LLQ	lower limit of quantitation
LS	least-squares
LSM	least-squares mean
MAR	Missing at random
MATE	multidrug and toxin extrusion
max	maximum
min	minimum
MMRM	mixed-effects model with repeated measures
CCI	[REDACTED]
N/A	not applicable
CCI	[REDACTED]
NC	Not calculated
ND	Not done
CCI	[REDACTED]
NS	No sample

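### The liver-fat Emax section labels a placebo-adjusted ratio as a percent change from baseline, and gives no reference for the 25% and 30% lowering doses

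*SAP*

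**What the plan says.** All the main statements are in the Dose Response Modeling part of SAP Section 5.2.

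- Purpose: the Emax model "will be used to characterize the %change from baseline dose-response relationship of whole liver fat in Part 2". The left side of the displayed equation is change from baseline.
- Response: "The natural log transformed relative ratio from baseline response at the end of treatment period will be modeled with dose as a continuous variable", with log baseline liver fat as a covariate.
- Back-transformation: "The posterior means and 80% credible intervals of the placebo-adjusted effect estimates at each dose will be exponentiated". The same sentence names the result: the estimates are "exponentiated to obtain the predicted values of %change from baseline".
- Target doses: "the doses that result in 25% and 30% liver fat lowering will be identified along with their 80% credible intervals". No reference is attached to the lowering.

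E0 is a model parameter in its own right. SAP Appendix 2 defines it as "Efficacy at 0 dose level; also treated as placebo effect". Nothing visible fixes it at zero. Protocol Section 4.2.3.1 expects 8 pooled placebo participants to inform it, alongside 8 per active dose.

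**The concern.** The section states one quantity as its aim (change from baseline), computes another (effect relative to placebo), and gives the second the name of the first. On the log scale the two differ by exactly E0. A table built to the text would show placebo-adjusted values under a from-baseline heading.

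The target doses inherit the uncertainty. The stated purpose of the model points to baseline, while the estimates carried forward are placebo-adjusted. Two competent analysts could each follow the text and report different doses from the same fit. SAP Section 5 leaves named sponsor staff, including the statistician, unblinded during the study. An unstated reference is therefore better settled before the fit than after it.

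**Working it through.** The plan gives no figure to reproduce here. The check is algebra, followed by an illustration on assumed values.

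**Definitions.** Let y(d) be the model for ln(end of treatment / baseline):

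y(d) = E0 + Emax × d^Hill / (ED50^Hill + d^Hill)

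Let D(d) = y(d) − E0, the placebo-adjusted effect.

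**Step 1: what exponentiation returns.**

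- exp(D) is the active-to-placebo ratio of the geometric mean ratios to baseline.
- 100 × (exp(D) − 1) is the placebo-adjusted percent change.
- 100 × (exp(E0 + D) − 1) = 100 × (exp(y) − 1) is the percent change from baseline.

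For D = −0.3567, exp(D) = 0.70, which is a 30% lowering relative to placebo. The SAP describes exp(D) but names the third quantity.

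**Step 2: the gap between the two references.** If placebo changes by p, then exp(E0) = 1 + p, and the percent change from baseline is 100 × ((1 + p) × exp(D) − 1).

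| Assumed placebo change | 25% placebo-adjusted lowering, from baseline | 30% placebo-adjusted lowering, from baseline |
|---|---|---|
| −10% | −32.5% | −37.0% |
| −5% | −28.75% | −33.5% |
| 0% | −25.0% | −30.0% |
| +5% | −21.25% | −26.5% |

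**Step 3: the dose for 30% lowering.** Assume Hill = 1 and a maximum placebo-adjusted lowering of 40%, 50% or 60%, so that Emax = ln(0.60), ln(0.50) or ln(0.40). The required D is ln(0.70) on the placebo-adjusted scale and ln(0.70) − E0 on the from-baseline scale. With f = D / Emax, dose / ED50 = f / (1 − f).

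Example with a maximum of 50% and a placebo fall of 10%:

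- Placebo-adjusted: f = −0.3567 / −0.6931 = 0.5146, so dose / ED50 = 0.5146 / 0.4854 = 1.06.
- From baseline: D = −0.3567 + 0.1054 = −0.2513, f = 0.3626, so dose / ED50 = 0.3626 / 0.6374 = 0.57.
- Ratio of the two doses: 1.86.

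Doses below are multiples of ED50. The ratio is the placebo-adjusted dose over the from-baseline dose.

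| Maximum lowering | Placebo-adjusted dose | From baseline, placebo −10% (ratio) | From baseline, placebo −5% (ratio) | From baseline, placebo +5% (ratio) |
|---|---|---|---|---|
| 40% | 2.31 | 0.97 (2.39) | 1.49 (1.56) | 3.85 (0.60) |
| 50% | 1.06 | 0.57 (1.86) | 0.79 (1.35) | 1.41 (0.75) |
| 60% | 0.64 | 0.38 (1.69) | 0.50 (1.28) | 0.79 (0.80) |

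At no placebo change every ratio is 1. The 25% dose behaves alike, with ratios of about 1.8 to 2.3 at a 10% placebo fall. These are multiples under assumed parameters and say nothing about which dose is suitable.

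**The case against.** Four points can fairly be made on the other side.

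1. The missing subtraction of 1 and multiplication by 100 is probably shorthand. A value of 0.70 would be recognised as a 30% reduction. This stands, and that part of the wording carries little weight. It does not excuse the baseline label, because a programmer who supplies the percent step still has a number relative to placebo.

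2. A reader might infer that the 25% and 30% doses are on the wrong scale. The text does not support that. It names no reference for them, and since the preceding estimates are placebo-adjusted, a placebo-adjusted reading is natural. The opening purpose statement points to baseline instead. This is an omission and an ambiguity; no wrong reference is stated.

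3. Relevant material is redacted: the content of Appendix 3, to which the section defers for its Bayesian method, and the section between 6.2 and 6.4. The abbreviation list still carries response ratio and geometric mean ratio, so ratio-scale quantities are used somewhere. Those pages may define the transform or the target. This limits what can be said about the doses. The Section 5.2 sentence would still need correcting, because it would then conflict with them.

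4. A reader might also infer a general two-fold dose error that feeds later dose selection. Neither part is in the documents. A ratio near two needs roughly a 10% placebo fall together with the assumed curve, and no visible text says how the target doses will be used. The model is fitted only if the data allow, clinical-activity endpoints are tertiary (Protocol Section 9.4.4.1), and SAP Section 5.1 sets no decision rules. E0, Emax, ED50 and slope are all to be reported, so approximate point estimates can be rebuilt on either scale. The credible intervals cannot be rebuilt exactly without the joint posterior.

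**Conclusion.** The concern holds for the labelling. As written, the rule produces a ratio relative to placebo and calls it a percent change from baseline; the two references agree only when E0 is zero. With 8 placebo participants expected, an estimate of exactly zero is unlikely. No visible text corrects the sentence.

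For the target doses, the finding is narrower: the visible text gives no reference, and redacted pages may give one.

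The size is conditional. With Hill = 1 and a maximum lowering of 40-60%, the choice of reference moves the 30% dose by a factor of about 1.3-1.6 at a 5% placebo fall and 1.7-2.4 at 10%. It makes no difference at 0%, and it moves the dose in the opposite direction if placebo rises. The primary safety and PK conclusions are untouched.

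**What to change.** In the Dose Response Modeling part of SAP Section 5.2:

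- Write the left side of the equation as y(d), the model for ln(end of treatment / baseline), and define D(d) = y(d) − E0.
- Report placebo-adjusted percent change as 100 × (exp(D) − 1) and percent change from baseline as 100 × (exp(E0 + D) − 1), each under its own label. Obtain the credible limits by applying the same transforms to the joint posterior of E0 and D.
- Before the fit, name one reference, baseline or placebo, for the 25% and 30% lowering doses, and check that Appendix 3 agrees.

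The cost is about two sentences and a table label. No new data or additional model fit is needed.

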### **5.3. Methods to Manage Missing Data**

#### **5.3.1. Safety Data:**

For the analysis of safety endpoints, the sponsor data standard rules for imputation will be applied.

#### **5.3.2. Pharmacokinetics Data:**

Methods to handle missing PK data are described below.

Concentrations Below the Limit of Quantification:

In all data presentations (except listings), concentrations below the limit of quantification (BLQ) will be set to zero. (In listings, BLQ values will be reported as “<LLQ”, where LLQ will be replaced with the value for the lower limit of quantification.)

Deviations, Missing Concentrations and Anomalous Values:

In summary tables and plots of median profiles, statistics will be calculated having set concentrations to missing if 1 of the following cases is true:

1. A concentration has been collected as ND (ie, not done) or NS (ie, no sample),
2. A deviation in sampling time is of sufficient concern or a concentration has been flagged anomalous by the pharmacokineticist.

Note that summary statistics will not be presented at a particular time point if more than 50% of the data are missing.

Pharmacokinetic Parameters:

Actual PK sampling times will be used in the derivation of PK parameters. If a PK parameter cannot be derived from a subject's concentration data, the parameter will be coded as NC (ie, not calculated). (Note that NC values will not be generated beyond the day that a subject discontinues.) In summary tables, statistics will be calculated by setting NC values to missing; and statistics will be presented for a particular dose with  $\geq 3$  evaluable measurements or at least 50% of the data are available depending on the parameter.

If an individual subject has a known biased estimate of a PK parameter (due for example to an unexpected event such as vomiting before all the compound is adequately absorbed from the gastrointestinal tract), this will be footnoted in summary tables and will not be included in the calculation of summary statistics or statistical analyses.

CCI

## 6. ANALYSES AND SUMMARIES

The data from each of the 3 Parts will be analyzed and reported separately in a single CSR issued at the end of this study.

### 6.1. Primary Endpoint(s)

The primary endpoints in Part 1 and Part 2 are related to safety/tolerability whose analyses are described Section 6.6.

The primary endpoints in Part 3 are the plasma PK endpoints whose analyses are described in Section 6.2.

### 6.2. Secondary Endpoint(s)

The secondary endpoints (in Part 1 and Part 2) as well as the primary endpoints (in Part 3) are related to PK and are described herein. The following analyses will utilize the PK Concentration and PK Parameter analyses sets defined in [Table 6](#) in Section 4.

No formal inferential statistics will be applied to the plasma PK data from Part 1 and 2. In Part 3, if conducted, the statistical comparison of plasma PK under high-fat/high-caloric state (test) versus fasted (reference) condition is envisioned.

Plasma parameters will be summarized using the descriptive statistics specified in Table 7 and urine PK parameters will be summarized using the statistics specified in Table 8.

**TABLE 7. PLASMA PK PARAMETERS TO BE SUMMARIZED DESCRIPTIVELY**

Parameter	Summary Statistics
AUC inf , AUC last , C max , AUC inf(dn) , AUC last(dn) , AUC tau , AUC tau(dn) , C max(dn) , CL/F, V z /F, C min , PTR, AUC tau , C av , R ac,AUCtau , and R ac,Cmax	N, arithmetic mean, median, %CV, standard deviation (SD), minimum (min), maximum (max), geometric mean and geometric %CV
T max , T lag	N, median, min, max.
t 1/2	N, arithmetic mean, median, %CV, SD, min, max.

**TABLE 8. URINE PK PARAMETERS TO BE SUMMARIZED DESCRIPTIVELY**

Parameter	Summary Statistics
Ae tau , Ae tau % and CL r	N, arithmetic mean, median, %CV, SD, min, max, geometric mean and geometric %CV.

- **Part 1 (Single, Escalating Doses):**
- Plasma concentrations of PF-07202954 will be descriptively summarized and plotted by nominal PK sampling time and dose.

- The plasma PK parameters  $AUC_{inf}$ ,  $C_{max}$ ,  $AUC_{last}$ ,  $T_{max}$ ,  $T_{lag}$ ,  $CL/F$ ,  $V_z/F$ , and  $t_{1/2}$  will be summarized descriptively by dose;

[REDACTED]

[REDACTED]

- **Part 2 (Repeated, Escalating Doses):**

- Plasma concentrations of PF-07202954 will be descriptively summarized and plotted by nominal PK sampling time, day, and dose;
- The plasma PK parameters  $AUC_{tau}$ ,  $C_{max}$ ,  $T_{max}$ ,  $T_{lag}$ ,  $t_{1/2}$ ,  $C_{min}$ ,  $C_{av}$ ,  $PTR$ ,  $CL/F$ ,  $V_z/F$ ,  $R_{ac,AUC_{tau}}$ , and  $R_{ac,Cmax}$ , and the urine PK parameters  $Ae_{tau}$ ,  $Ae_{tau}\%$ , and  $CL_r$  will be summarized descriptively by dose and day as applicable;

[figure not shown]
[figure not shown]
[REDACTED]

- Median morning trough (predose) plasma concentrations will be plotted by day (all doses on the same plot) in order to assess the attainment of steady state.
- **Part 3 (Single-Dose Food Effect, if conducted):** To compare PF-07202954 exposures following high-fat/high-caloric meal (Test) versus following an overnight fast (Reference) natural log-transformed  $C_{max}$ ,  $AUC_{last}$ , and  $AUC_{inf}$  (if data permit) will be analyzed using a mixed effects ANOVA described in Section 5.2. Estimates of the adjusted mean differences (Test-Reference) and the corresponding 90% CIs will be obtained from the model. The adjusted mean differences and 90% CIs for the differences will be exponentiated to provide estimates of the ratio of adjusted geometric means (Test/Reference) and 90% CIs for the ratios.

**In addition for Part 3 –**

- Plasma concentrations of PF-07202954 will be descriptively summarized and plotted by nominal PK sampling time and treatment;
- The plasma PK parameters  $AUC_{inf}$ ,  $C_{max}$ ,  $AUC_{last}$ ,  $T_{max}$ ,  $T_{lag}$ ,  $CL/F$ ,  $V_z/F$ , and  $t_{1/2}$  will be summarized descriptively by treatment;
- For  $AUC_{inf}$ ,  $C_{max}$ , and  $AUC_{last}$ , box and whisker plots will be presented by treatment and overlaid with geometric means.

CCI

100%

95%

90%

95%

90%

95%

90%

95%

90%

[figure not shown]
[figure not shown]
[figure not shown]
95%

90%

95%

CCI

[REDACTED]

[REDACTED]

[REDACTED].

#### **6.4. Subset Analyses**

No subset analyses will be performed.

#### **6.5. Baseline and Other Summaries and Analyses**

Data will be reported separately for each part of this 3-part study in accordance with the sponsor's reporting standards.

##### **6.5.1. Baseline Summaries**

Demographic data collected at screening will be reported as part of the standard baseline summary tables. A breakdown of demographic data will be provided for age, race, weight, and body mass index.

##### **6.5.2. Study Conduct and Participant Disposition**

Participant evaluation groups will show end of study participant disposition. The presentation will include counts of participants analyzed for pharmacokinetics, and for safety. Frequency counts and percentages will be supplied for participant discontinuation(s) by treatment.

##### **6.5.3. Concomitant Medications and Nondrug Treatments**

All prior and concomitant medication(s) as well as non-drug treatment(s) will be provided in listings.

##### **6.5.4. Screening Data**

These data will not be recorded in the study database, and therefore will not be listed.

#### **6.6. Safety Summaries and Analyses**

No formal analyses are planned for the standard safety data.

The safety endpoints detailed in Section 6.6.5 will be listed and summarized separately for each part of the study and in accordance with sponsor reporting standards based on the safety population (as defined in Section 4, Table 6), with more details provided below.

Medical history and physical examination information, as applicable, collected during the course of the study will be considered source data and will not be required to be reported, unless otherwise noted. However, any untoward findings identified on physical examinations conducted during the active collection period will be captured as AEs, if those findings meet the definition of an AE. Data collected at screening that are used for

inclusion/exclusion criteria, such as laboratory data, ECGs, and vital signs, will be considered source data, and will not be required to be reported, unless otherwise noted.

#### **6.6.1. Treatment Emergent Adverse Events**

Treatment emergent adverse events will be reported in accordance with the sponsor reporting standards.

#### **6.6.2. Laboratory Data**

Laboratory data will be listed and summarized by treatment in accordance with the sponsor reporting standards. Baseline is as defined in Section 3.5.2.

#### **6.6.3. Vital Signs**

##### **Parts 1 and 2 only**

Absolute values and changes from baseline in supine systolic and diastolic blood pressure and pulse rate will be summarized by treatment and time postdose, according to sponsor reporting standards. Tables will be paged by parameter. Baseline is as defined in Section 3.5.3.

Mean changes from baseline for supine systolic and diastolic blood pressure and pulse rate will be plotted against time postdoses. On each plot, there will be 1 line for each treatment, all treatments on the same plot including the placebo. Corresponding individual plots of changes from baseline will also be produced for each treatment.

For supine systolic and diastolic blood pressure and pulse rate, the differences between each dose and placebo (dose – placebo) will be summarized (N, mean, 90% CI) and plotted (mean) for each dose and time postdose (including baseline).

##### **Parts 1, 2 and 3 (if conducted)**

Maximum absolute values and changes from baseline for vital signs will be summarized descriptively by treatment using categories as defined in Appendix 1. Numbers and percentages of subjects meeting the categorical criteria will be provided. All planned and unplanned postdose timepoints will be counted in these categorical summaries. All values meeting the criteria of potential clinical concern will be listed.

Maximum increase or decrease in vital signs will also be summarized; all planned and unplanned postdose timepoints will be included in these summaries.

#### **6.6.4. Electrocardiograms**

##### **Parts 1 and 2 only**

Absolute values and changes from baseline for the ECG parameters QT interval, HR, QTcF interval, PR interval, and QRS complex will be summarized by treatment and time using sponsor reporting standards. Tables will be paged by parameter. Baseline is as defined in Section 3.5.4.

Mean changes from baseline in QT, heart rate and QTcF will be plotted against time postdose. On each plot there will be 1 line for each treatment, all treatments on the same plot including the placebo. Corresponding individual plots of changes from baseline will also be produced for each treatment.

In addition for QTcF, heart rate and QT, the differences between each dose and placebo (dose – placebo) will be summarized and plotted (N, mean, 90% CI) for each dose and timepoint (including baseline).

Changes from baseline in QTcF will be plotted separately against drug concentrations. This will be a scatter plot for all observations where QTcF and drug concentration are recorded. Placebo data will also be included (with drug concentration set to zero). Different symbols will be used for each treatment.

In addition, an attempt may be made to explore and characterize the relationship between plasma concentration and QT interval length using a PK/PD modeling approach. If a PK/PD relationship is found, the impact of participant factors (covariates) on the relationship may be examined. However, this analysis will not be presented in the CSR.

